Comparison Condition: Group Health Education: The Group Health Education (GHE) condition is a 14-session, highly structured educational intervention providing general information on health problems that are common among the general OEF/OIF/Persian Gulf cohort including sleep and sleep problems, physical activity and exercise, and alcohol and drug use, as well as general guidelines for improving health behavior in these areas. Areas of focus in MFG-mTBI-C such as coping with Veterans' memory problems or couples and family readjustment issues are explicitly not addressed in GHE. Each session follows the same structure, beginning with a presentation of the objectives for the current session and a brief review of material from the previous session before introducing the session's topic and presenting information on two to six major points. In order to limit opportunities for group interaction and development of group cohesion, GHE utilizes a traditional didactic model with information delivered by the educator in a classroom or lecture setting (where all chairs face the educator), where the information provided is general and broad-based rather than focused on individual participants' concerns. To avoid overlap with MFG problem-solving skills training. individual health problems will not be discussed: participants will be referred to their provider or supplied with a referral as needed. By contrast, MFG-mTBI-C delivers skills training in a roundtable setting where all group members are encouraged to join in problem-solving exercises, the educator's approach is collaborative and materials are drawn from the everyday problems brought in by members, designed to foster group cohesion and support. Consistent with an educational model, handouts summarizing session material are provided in GHE-C but homework is assigned only in MFG-mTBI-C, as an integral feature of skills training and of our adaptation of multifamily group for mTBI where rehearsal and repetition are critical components of skills acquisition. Table 6 shows the key structural-conceptual differences between conditions, while Table 7 summarizes the overall structure of the two conditions, including the different phases, components and basic material delivered in each intervention. Table 7 demonstrates the 2 conditions are identical in # sessions and overall structure (multifamily group sessions following individual couples "Joining" sessions), but differ in treatment strategies (skills training vs. general education without reference to or problem-solving about participants' individual health concerns/behavior. As with MFG-mTBI-C, the educator joining with the couple is also the group leader. To accommodate difficult schedules that often include work, school, and/or childcare, we offer participants to call-in to groups from a private space, such as a bedroom or private office, to maintain confidentiality.

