
Table 6: Comparison of MFG-mTBI-C and Control Treatment (GHE)

Treatment Component	MFG-mTBI-C	GHE (Control)	
Therapeutic Strategy	Skills training	Information only	
Contents	Compensation for TBI-related deficits in emotion processing, memory/planning	Building a healthy lifestyle	
Target Group	OEF/OIF/Persian Gulf Veterans with TBI/partners	All OEF/OIF/Persian Gulf Veterans/partners	
Use of Group Dynamics/ Cohesion	Social support promoted:  Entire group participates in problemsolving for each couple and gives support and encouragement	Social support minimized:  Because individual health issues are not discussed, education is general and group interaction minimized	
Therapeutic Stance	Educator stance is collaborative	Educator stance is didactic	
Room Set-up	Round table	Lecture style (all chairs face forward)	
Source of Material	Drawn from everyday problems brought in by group members	Supplied by educator	
Homework	Assigned and reviewed and the start of the following session	Handouts but not homework provided	

Table 7: Comparison of MFG-mTBI-C and Control Treatment (GHE)

Treatment Component	MFG-mTBI-C	# sessions	GHE (Control)	# sessions
Joining	Couples-tailored Education:* Normalization of couples conflict, misattribution of TBI deficits corrected.  Skills Training: Recommend 1+ compensatory strategies, basic communication training exercise.  Formulation of problems in coping & communication patterns	2(3)**	Standard Couples Intake: History of Veteran, partner and couple, focusing on current health, activities, sleep patterns, diet, medications and other health behaviors. No skills training, cognitive interventions or formulation of couples' functioning.	2(3)**
Multifamily Group Sessions	Educational Workshop: TBI: pathogenesis, behavioral sequelae, comorbidities, treatment, prognosis and family impact. Structure and function of multifamily group, how it can help.	2	Health Education Introduction: Structure and rationale for intervention. Rules of conduct. Overview of topics to be covered.	1
	Problem-solving Sessions: Skills training: Problem-solving designed to address specific problems associated with mTBI. Compensatory strategies for memory problems, planning. Disability-adapted communication training.	12	Group Health Education: Information provided to promote healthy living in areas relevant for Veterans and partners (sleep hygiene, nutrition, use of alcohol, drugs, safe exercise). Personal health concerns not discussed-referred to provider.	13

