missing data points and unequal intervals between testing occasions. Choices of variancecovariance structures to account for within-subject correlation will be made based on the AIC, BIC, or likelihood ratio statistic. All principal analyses will be conducted based on the intentionto-treat principle in which any participant randomized to a treatment arm remains in it regardless of adherence to or completion of treatment. We will measure the level of participation, and will conduct a sensitivity analysis that assesses the stability of the conclusions from this study with an intention-to-treat analysis versus an analysis that takes into account level of adherence. With multiple time points and variables representing outcomes at both the individual and couples level, the planned analyses involve multiple comparisons raise concerns about the increased likelihood that any single outcome will be found to be statistically significant based on chance alone. In order to minimize this risk, we have carefully selected a limited number of outcomes and clearly designated primary, secondary and exploratory outcomes. Our primary outcomes for the Veteran and for the caregiver are each represented by a single measure. For models evaluating the effect of treatment assignment on constructs represented by more than one measure, e.g., Veteran Emotion Regulation and Interpersonal Skills, we will employ Bonferroni's correction to adjust each observed p-value by the number of tests performed and have calculated power on this basis (see power calculations below).

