### Tests of Specific Study Hypotheses:

### **Primary Hypotheses:**

Hypothesis 1: Veterans with mTBI treated with 6 months of multi-family group for couples (MFG-mTBI-C) will show improved community integration (primary outcome), and improved anger management and use of social support (secondary outcomes) compared with those treated in a health education group without training in communication skills or compensatory strategies; Changes in the primary study outcomes (Sydney Psychosocial Reintegration Scale) from baseline for each treatment group at each time point will be examined using paired t-tests or Wilcoxon signed-rank tests as appropriate. Differences in changes in mean Sydney scores from baseline between two treatment groups will be compared using t-tests or Wilcoxon rank-sum tests as appropriate at each time point. Linear mixed models will be used to examine changes in scales over time and to examine whether the effects of MFG-mTBI-C on the Sydney and secondary Veteran outcomes (DERS and social support scales) vary with time and study sites adjusted for the time-dependent treatment, imbalanced baseline prognostic factors (if applicable), and control variables relating to combat/ injury exposure (mechanism of injury (blast vs. other), # deployments, # TBI's and degree of exposure to war zone violence/threats). In addition, Spearman correlation coefficients will be used to assess associations of changes in the Sydney with changes in Veteran symptoms from baseline at each time point and to examine whether degree of associations increases over time among Veterans treated with MFG-mTBI-C. If significant patterns over time are observed in any of these variables, mixed models will then be used to examine the effects of the variables identified on CI change over 6 months post treatment.

Hypothesis 2: Caregivers whose Veteran spouse/partners are treated with MFG-mTBI-C will show reduced burden (primary caregiver outcome) over the course of treatment and in the 6-month follow-up period relative to caregivers whose Veteran partners are treated in a health education group. The analytic plan proposed in Hypothesis 1 will be used for assessing effects of MFG-mTBI-C on changes in the CBI.

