Analyses to Determine Generalizability of Results: Although the rate of refusal in the pilot study was relatively low (28.6% of caregivers of consenting patients), we will compare the baseline characteristics (e.g., age, sex, education) of the study caregiver population to those that declined participation, and will evaluate reasons for refusal using questions adapted from our Family Service Needs and Treatment Preferences Scale (FANS-[name] et al., 2009, Appendix A). Missing data and loss to follow-up are usually concerns in longitudinal studies presenting problems in interpretation with any approach. The validity of the resulting inferences depends critically on the underlying mechanism that generates the missing observation. If the mechanism for missing data is not a function of the underlying missing data, then no adjustment is necessary. Data that are missing at random will yield estimates from the likelihood-based methods that are valid and efficient, provided the model assumed for the data distribution is correct. However, when missing data are related to study treatment or outcomes of interest. parameter estimates and resulting tests on hypotheses will be biased without further adjustment. In this study, data will be stratified according to their missing pattern (e.g., early termination, late termination, and complete follow-up); variables based on these groups will be used as model covariates, allowing us to examine the effects of missing-data patterns on outoutcome measures. Overall estimates can be obtained by averaging over the missing patterns. Multiple imputations will be used if missing data rates are observed to differ across observed covariates.

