## 5.7 Withdrawal of Subjects

Participants can refuse to participate in the study initially or can withdraw from the study at any time after giving consent, which will not interfere with treatment if they are a patient. Subjects that withdraw will be asked for permission to contact them to complete assessments remaining in the study. Any participant (whether a Veteran or spouse/partner) found to have violated the

confidentiality of the group or who causes distress to others, e.g., through verbal aggression or repeated and deemed irremediable disruptions to the group activity after clinician intervention, will be excluded from the intervention and from the study.

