## 7.0 Privacy and Confidentiality

Once a Veteran consents to participate in the study, the research assistant will then seek permission to contact the Veteran's spouse/partner. After the Veteran gives informed consent and permission to contact his/her spouse/partner, we shall first screen them to determine eligibility. Once eligibility has been confirmed, the RA will contact the spouse/partner by telephone to describe the project, answer questions, and invite them to meet with him/her to explain the study. The initial interview will begin with the interested spouse/partner, to describe the project, and to determine who is eligible for the study as the primary caregiver. We shall use a self-rating scale that asks about frequency of contact, involvement and care-giving responsibility for this purpose. Informed consent will then be sought from this person. We are only enrolling Veterans who regularly receive services from or work at the JJP VAMC, VAMHCS, or VA NYHHS mental health clinic, so the environmental experience will not differ

from their usual routine. The individual and group sessions will be conducted in the private setting of a closed office or group room. Any participant (whether Veteran or spouse/partner) found to have violated the confidentiality of the group or who causes distress to others, e.g., through rudeness or verbal aggression, will be excluded from the intervention and from the study.

Privacy during interviews of patients and caregivers will be maintained by using offices that are not shared and by keeping the door closed. Questionnaires can be administered over the phone only if the Veterans or spouse/partner is alone in a private room at his/her residence, and the research staff member is in a private office or room.

All investigators, the project coordinator and research assistants will be eligible to review individuals' paper research records at the study sites. However no individual's paper research records will be transferred from the study site where the data was collected. Representatives of the USAMRMC are eligible to review research records.

The research team will follow the same reporting requirements as the clinicians providing the research intervention regarding sensitive information to be reported to New York State authorities. Any information on child abuse provided to a research assistant during interviewing or to other research team members will be reported to Child Protective Services within 24 hours.

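### Removal from the group for conduct also ends study participation, so outcomes are lost after randomization that the trial could still collect

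*Combined protocol and SAP*

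**What the plan says.** Section 5.7 treats two kinds of early ending differently.

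- **Voluntary withdrawal:** "Subjects that withdraw will be asked for permission to contact them to complete assessments remaining in the study".
- **Removal for conduct:** a Veteran or partner who breaches confidentiality or causes distress to others "will be excluded from the intervention and from the study". No request for the remaining assessments follows.

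Section 7.0 (Privacy and Confidentiality) states the same rule with different examples of conduct: a person who causes distress, for instance "through rudeness or verbal aggression, will be excluded from the intervention and from the study". The examples in Section 5.7 are verbal aggression and repeated disruption judged irremediable after a clinician has intervened.

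Section 5.6 (General Approach) sets the analysis principle: "any participant randomized to a treatment arm remains in it regardless of adherence to or completion of treatment".

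**The concern.** Stopping someone's attendance at a group does not require stopping their outcome assessments. The protocol already separates the two for people who withdraw, but not for people whom the study removes. Those outcomes are then missing because of a decision made after randomization.

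Three features of the design make it doubtful that the loss would be unrelated to the comparison:

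- Verbal aggression is a trigger for removal. Hypothesis 1 names anger management as a secondary Veteran outcome, and Hypothesis 3 treats emotion regulation as a mediator.
- The arms differ in how much opportunity they give for such conduct. In MFG-mTBI-C, Table 6 says "Entire group participates in problemsolving for each couple". For the control, Section 5.1 says "In order to limit opportunities for group interaction and development of group cohesion, GHE utilizes a traditional didactic model".
- The documents do not say who decides on removal. Each educator conducts only one intervention and the PI holds the assignment list (Section 5.1), so the people best placed to decide know the arm.

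The rule applies to either member of the couple and is silent on the other. One removal could therefore cost both the Veteran's community integration outcome (Sydney) and the partner's burden outcome (CBI).

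**Working it through.** The plan gives no count or rate of removals, so there is no figure of its own to reproduce. The main check compares the passages; the arithmetic only illustrates scale.

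**Comparison of passages**

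1. Section 5.6 keeps a randomized participant in the assigned arm whatever their adherence or completion.
2. Section 5.7 seeks the remaining assessments after withdrawal. After removal, Sections 5.7 and 7.0 end study participation and provide for no assessment.
3. Outcomes are measured pre-treatment, post-treatment and at 6 months (Section 5.1, Table 5). Someone removed during the group phase and not assessed again has no outcome after the groups begin.
4. Section 5.6 (Analyses to Determine Generalizability of Results) recognises that estimates are biased without further adjustment "when missing data are related to study treatment or outcomes of interest". It plans covariates for missing-data patterns, averaging over patterns, and multiple imputation if missing-data rates differ across observed covariates. The example patterns are early termination, late termination and complete follow-up, so they are defined by timing and not by cause. A removed person with no follow-up measure gives no information on their own change. Averaging over patterns then needs an assumption about that change, and multiple imputation normally assumes data missing at random.
5. The DSMB report (Section 6.0) lists removals for clinical deterioration. Removals for conduct are not itemised.

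**Illustration of size**

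Let a fraction *f* of an arm be removed, with mean change δ SD worse than that arm's average. The raw mean of those retained is then too favourable by δ × *f*/(1 − *f*). The bias in the difference between arms is

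δ × [*f*₁/(1 − *f*₁) − *f*₀/(1 − *f*₀)],

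where 1 is MFG-mTBI-C and 0 is GHE. All rates and gaps below are assumptions.

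- *f*₁ = .05, *f*₀ = .01 (about 4 and 1 of the planned 75 per arm): .0526 − .0101 = .0425. The bias is .021 SD at δ = 0.5 and .043 SD at δ = 1.
- Stress case, *f*₁ = .10, *f*₀ = .02: .1111 − .0204 = .0907. The bias is .045 SD at δ = 0.5 and .091 SD at δ = 1.
- Equal rates and equal gaps: the bias is 0.
- Rates reversed between arms: the same sizes with the opposite sign.

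With 1 of 75 removed from MFG-mTBI-C, none from GHE, and a gap of 0.5 to 1.5 SD between removed and retained, the bias is (1/75) × gap, or .007 to .02 SD.

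The loss of power is minor. For a 0.5 SD difference and no other attrition, power is about .86 with 75 per arm and about .84 if 8 couples are lost in total.

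**The case against.** The strongest reply has five parts.

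- **Intention-to-treat is not contradicted outright.** A reader might infer that removed participants are deleted from the analysis set. The documents do not say so. The sentence in Section 5.6 concerns which arm a person belongs to, and exclusion from the study is left undefined. The clear loss is later assessments. This stands, so the point is about avoidable missing data and undefined wording.
- **The direction is not established.** A reader might infer that the rule takes poor responders mainly out of MFG-mTBI-C and so favours it. That is an inference from the format of the groups. The documents give no removal rates and no outcomes of removed people. The rule also covers confidentiality breaches and partners. The comparison is of change from baseline, and an aggressive participant may have a poor level without a poorer change. This stands.
- **Removals may be rare.** The pilot, an open trial of the interactive format, had about 10% attrition in total (Section 5.6, power calculation), and 92% of Veterans who started treatment completed it (Section 5.1). The stress case would put all-cause pilot attrition down to conduct alone. Section 5.4 also excludes severe inter-partner violence, active psychosis and recent substance abuse. This stands, and the lower scenario is the more reasonable illustration.
- **There is a missing-data plan.** It is relevant, and the formula above ignores any modelling of baseline or pattern. It softens the problem but cannot supply outcomes that were never measured.
- **The two sections state one criterion.** Both cover breaching confidentiality or causing distress, and what differs is the examples. This stands, but the examples suggest different thresholds and sites could apply them differently.

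**Conclusion.** The point holds as a gap in the text with a small, conditional effect. Following Sections 5.7 and 7.0 as written gives up post-randomization outcomes for a reason that may relate to both outcome and arm, and that sits badly with the stated intention-to-treat principle. The planned missing-data methods cannot repair this without untestable assumptions.

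Direction and size are unknown. About .02 to .04 SD in favour of MFG-mTBI-C rests entirely on assumed removal of 5% versus 1% and an assumed gap of 0.5 to 1 SD, and applies to raw means. It falls to zero with equal rates and gaps. These SD figures cannot be set directly against the plan's effect sizes of .5 to .7, which Section 5.6 defines as (mt − mc)/mc. The documents support neither deletion of collected data nor a demonstrated bias towards MFG-mTBI-C. The change is worth making because it is cheap and removes the question.

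**What to change.** In Sections 5.7 and 7.0:

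- Limit the exclusion to the intervention.
- State that the removed participant and the partner will be asked for permission to complete the post-treatment and 6-month assessments outside the group. Questionnaires can be done by telephone where the privacy conditions of Section 7.0 are met. Other assessments can be done at the locations that the end of Section 5.3 allows (affiliated clinics, the home or a neutral place).
- State that all randomized participants are analysed in their assigned arm.

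Reporting removals by arm and reason would let readers judge how much this matters. The sponsor must reconcile the differing examples of conduct in Sections 5.7 and 7.0; this review does not suggest what the threshold should be.

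The cost is protocol wording and a few more follow-up contacts. The telephone provision covers questionnaires only, so some in-person neuropsychological tests may still be missed.

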## 6.0 Reporting

This project will be monitored by a Data and Safety Monitoring Board (DSMB) because the Veterans have either been diagnosed with mTBI, a mild cognitive impairment, PTSD, and/or have reported moderate-severe PTS or CS. Thus, while the risk in this study is minimal, these Veterans can be considered a vulnerable population. The board will be composed of persons not affiliated with this pilot intervention who are experienced in various aspects of the conduct of clinical trials for persons with mTBI, or with research on PTSD or associated conditions. Because the safety risk is judged to be minimal, we propose to submit a quarterly report of aggregate data to DSMB members rather than attempt an interim analysis of efficacy and safety data by treatment assignment. The report will contain screening data, baseline demographics, retention data, number of participants removed due to clinical deterioration, serious adverse events data, as well as accruable status including projections and times to milestones. Based on this report, each DSMB member will complete a form making one of two recommendations: 1) continue recruitment as planned; or 2) schedule formal DSMB meeting immediately. If any DSMB member recommends a meeting, this will be scheduled within one week, minutes will be kept, the report will be reviewed with the PI, and the committee will vote on whether the study should: 1) continue recruitment unchanged; 2) continue with a protocol amendment; 3) stop recruiting pending further investigation. If, after this meeting, any DSMB member votes to stop recruitment, each site's IRBs will be informed. All SAEs will result in completion of an SAE reporting form and a verbal report to the Principal Investigators ([name]). Within 24 hours, the following additional individuals will be notified: 1) all Consulting Investigators and Senior Clinicians; 2) all Core Clinical Investigators; 3) The VA Institutional Review Board; 4) the DSMB. These same individuals will receive a copy of the SAE form within one week at which point a decision will be made whether to convene a meeting of the DSMB. Communication of recommendations and decisions from all parties are made back to the investigator in a timely manner. We will report all protocol amendments or changes in the informed consent to the VA IRB, as well as any temporary or permanent suspension of participant accrual.

[name] will chair the Advisory Board and Treatment Committee. She will supervise and meet with the VISN 5 study staff weekly and will participate in weekly conference calls with the VISN 2 South study sites to assess and report any unanticipated problems, serious adverse advents, or protocol deviations.

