Intervention Testing Procedures-Randomization and Maintaining Blind: Following informed consent enrollment, couples will be randomized to one of two treatment conditions (75 to each condition) within each VISN: 1) MFG-mTBI-C, or 2) GHE. To maximize adherence to intervention protocol and avoid inadvertent cross-contamination, each of the two educators at each site will conduct only one intervention, either MFG-mTBI-C or GHE. We will take precautions to ensure the RA's performing outcome assessments and other relevant persons are blind to study condition: 1. Subjects will be randomized to treatment condition using Proc Plan in SAS by an independent research staff member from another project who will place treatment assignments in separate envelopes according to the randomization sequence. To avoid recruitment and/or assessment bias, envelopes will be opened by the independent researcher after informed consent procedures in sequence, and assigned participants will be given a new # according to the randomization schedule; 2. The list linking participant code with treatment assignment will be maintained in a locked cabinet by the PI (who will not perform assessments) and by the study biostatistician (who is in a different location); 3. RA's performing assessments will be blind to educator assignment to treatment condition and will additionally be unaware that each educator is delivering only one treatment. 4. To make # 3 plausible, all educators (and other research staff) will participate in the initial training for both treatments. 5. The PIs will convey new assignments to the appropriate educator who will initiate contact to schedule Joining sessions. 6. All educators will deliver both treatments in closed rooms; 7. The rooms will be equipped identically, with a digital tape recorder; 8. The number and length of sessions will be standardized across conditions; 9. Both MFG-mTBI-C and GHE sessions will be recorded for adherence monitoring so that all participants will have identical files; 10. All data pertaining to session material (e.g., treatment notes) will be stored by educators in a locked or password-protected file separate from that used for assessment data; RA's will not have access to the session files. 11. Participants will be trained not to discuss study procedures except with their study educator or the PI, and study staff (educators and RA's) will only discuss study procedures and assignments with the PI or during supervision. 12. Veterans' VA clinicians will be blind to their treatment assignment; 13. Prior to data analysis, the biostatistician will add an electronic field for treatment group to the data base and the data analyst will be trained not to link assignment with ID code. Thus although RA's will be able to link participant names with ID codes needed for labeling and entering data, etc., they will be blind to treatment assignment using the above measures.

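### As written, the DSMB cannot compare harms between MFG-mTBI-C and GHE: its quarterly report is pooled, and nothing says that the individual SAE forms show the arm

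*Combined protocol and SAP*

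**What the plan says.** Section 6.0 (Reporting) sets up a DSMB because the Veterans may be regarded as vulnerable. It then limits what the board sees. The reason is "Because the safety risk is judged to be minimal", and the consequence is "we propose to submit a quarterly report of aggregate data to DSMB members rather than attempt an interim analysis of efficacy and safety data"; the sentence closes by making clear that the analysis declined is one split by arm. The safety content of the report is the "number of participants removed due to clinical deterioration, serious adverse events data", alongside screening, baseline, retention and accrual information.

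The report drives the board's routine decision: "Based on this report, each DSMB member will complete a form making one of two recommendations", namely to continue recruitment or to call a formal meeting at once. One member's request is enough for a meeting within a week. There the report is gone through with the PI, and the board votes to continue, amend or stop recruiting.

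A second route exists for SAEs. The DSMB is among those notified within 24 hours, and "These same individuals will receive a copy of the SAE form within one week", when it is decided whether the board should meet.

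Section 5.1 (Randomization and Maintaining Blind) governs access to the allocation: "The list linking participant code with treatment assignment will be maintained in a locked cabinet by the PI" and by the study biostatistician, who works at a different location. It adds: "Prior to data analysis, the biostatistician will add an electronic field for treatment group to the data base".

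**The concern.** The board votes on whether a trial in a vulnerable population should go on, but the plan gives it no comparison between the arms. The reason offered, low risk, is a good argument against a formal interim efficacy analysis. It is a weaker argument against a descriptive safety count by coded arm, which involves no test and spends no alpha.

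The arms differ in exposures that could bear on safety. Section 5.1 allows MFG-mTBI-C couples to re-enact a recent dispute in communication training. GHE leaves out couple and family readjustment issues and keeps group interaction low. Section 5.4 excludes only severe inter-partner violence. None of this shows that MFG-mTBI-C causes harm. It does mean that the contrast between arms is the informative safety comparison, and the independent board is not given it. The PI holds the assignment list and receives verbal SAE reports, so the PI can make that comparison during the trial.

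**Working it through.** The plan states no event rate, safety threshold or stopping boundary, so there is no figure to reproduce. The check has two parts.

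**1. What reaches the board, item by item**

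| Item | Route to the DSMB (Section 6.0) | Arm shown? |
|---|---|---|
| SAEs, counts | Quarterly report | No; by-arm analysis is expressly declined |
| SAEs, single cases | Notice within 24 hours, form within one week | Not stated; the form is not reproduced |
| Removals for clinical deterioration | Quarterly report, as a number | No |
| Withdrawals | Quarterly report, within retention data | No |

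Could the board work out the split itself? Section 5.1 names two holders of the list, the PI and the biostatistician, and the board is not one of them. The treatment field enters the database only before data analysis, so a routine extract during the trial would not carry it. Section 6.0 has the report reviewed with the PI at a formal meeting but provides for no disclosure by arm. The documents describe no closed report, coded-arm table or request procedure.

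For SAEs the supported statement is therefore that no by-arm tabulation is provided for. For removals and withdrawals it is that the only route described is pooled.

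**2. What a pooled count hides (illustration)**

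Inputs: 75 per arm, 150 in total (Section 5.1, Table 4). The event counts are assumptions. The test is a two-sided Fisher exact test on the table [a, 75 − a; b, 75 − b], where a and b are the numbers of participants with an event in each arm. The pooled rate is (a + b)/150.

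| Assumed events | Pooled rate | Split a:b | Fisher p |
|---|---|---|---|
| 8 | 8/150 = 5.3% | 4:4 | 1.00 |
| 8 | 5.3% | 6:2 | 0.28 |
| 8 | 5.3% | 7:1 | 0.063 |
| 8 | 5.3% | 8:0 | 0.006 |
| 10 | 10/150 = 6.7% | 5:5 | 1.00 |
| 10 | 6.7% | 8:2 | 0.098 |
| 10 | 6.7% | 9:1 | 0.018 |
| 12 | 12/150 = 8.0% | 6:6 | 1.00 |
| 12 | 8.0% | 10:2 | 0.031 |
| 15 | 15/150 = 10.0% | 8:7 | 1.00 |
| 15 | 10.0% | 12:3 | 0.027 |

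Within each assumed total the pooled report is identical, while the evidence of imbalance runs from none to appreciable. The p-values only describe how much information pooling removes. They are not a proposed monitoring rule.

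The table uses full enrolment. At about half enrolment (75/2, about 38 per arm), a 6:1 split gives p = 0.11 and 6:2 gives p = 0.26. An early by-arm table would usually be ambiguous and would need the board's judgement.

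**The case against.** The strongest reply is that this was a deliberate and disclosed choice. The text shows that review by arm was considered and declined as disproportionate for a psychoeducational group trial. Section 5.4 excludes severe partner violence, a suicide attempt in the past six months, and alcohol or drug abuse or dependence in the past three months, which lowers the risk. GHE couples also attend joint sessions, so harm need not fall in one arm. This stands in part: the point is a limitation of the monitoring plan, not an oversight or a contradiction.

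A reader might infer two stronger things that the documents do not support.

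- **That the board sees nothing but pooled data.** It does not: it also receives every SAE individually. Because the form is not reproduced, it cannot be ruled out that a narrative reveals the arm.
- **That no member would have grounds to call a meeting.** Any single member can trigger one, with no threshold. A high pooled count, more removals for deterioration, poor retention or one worrying SAE form could each prompt it, and nothing bars the board from then asking for the split.

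What remains is that a difference between arms, with an unremarkable total, would not itself be visible to the board.

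Two practical objections also stand. Event counts will be small, so chance differences will occur. Each arm is delivered in small groups by its own educators, so a leaked coded table might be decoded.

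**Conclusion.** The concern holds in limited form. As written, the board can respond to the overall level of harm and to single events. It cannot see an imbalance between MFG-mTBI-C and GHE in SAEs, removals for clinical deterioration or withdrawals. For SAEs this assumes that the forms do not disclose the arm, on which the documents are silent. For removals and withdrawals the text describes no other route.

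The practical size is unknown, because no expected rate is given and every numerical example above rests on assumed counts. Alpha, power, sample size and the primary estimate are not affected. The case for acting is that the change is cheap and serves participant safety, and that the minimal-risk reason does not extend to a descriptive coded-arm count.

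**What to change.** Add to Section 6.0 one closed table in each quarterly report, for DSMB members only, giving by coded arm (A/B) the numbers of SAEs, removals for clinical deterioration and withdrawals, with the number randomized to each arm as denominator. The biostatistician, who already holds the assignment list, prepares it. It carries no efficacy data and no test. State that it is descriptive and say how the board may request the code. Amend Section 5.1 so that this use of the list before the final analysis is permitted, and state whether the SAE form shows the arm.

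The cost is one short table per quarter and a separate confidential file that must be kept from investigators, educators and assessors. The board will also have to interpret small counts that sometimes differ by chance. If the file is kept closed, assessor blinding is untouched.
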